3.3 Sample size

The primary analysis will evaluate whether the use of ePOCT+ for case management of sick children in PHC facilities results in decreased antibiotic prescriptions (superiority analysis) at the initial consultation. Superiority in antibiotic prescription is defined as a relative decrease of $\geq 25\%$ in the proportion of children prescribed an antibiotic. We estimated a cluster size of 660 patients (monthly utilization of 220 – accounting for up to 30% non-adherence and/or loss to follow-up from 315 – over 3 months) and an intraclass correlation coefficient of 0.025. Non-adherence here is defined as HWs not using the application for all eligible patients that come to the HF for various reasons. To have 80% power to detect a 25% reduction in antibiotic prescription (from 35% to 26%), for a two-sided hypothesis test at alpha of

0.05, we would require a minimum of 11 clusters per arm. With 16 clusters per arm, over 3 months, we expect a total of 10,500 children in each study arm. Considering the pragmatic/adaptive nature of the study design, if a higher antibiotic prescription in the control arm is encountered (e.g. 45% or higher), each cluster study of 5-6 health facilities per study arm will be sufficiently powered to show a statistically significant reduction in the primary outcome. Sample size calculations were performed in R statistical software (version 4.0.3) using the CRTSize package (Rotondi, 2015).

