### 4.1 Primary intervention

[figure not shown]
As part of the primary intervention in Phase 1, the ePOCT+ tool, as well as the complementary e-learning and supervision tools, will be provided to HWs of 42 PHC facilities in Rusizi and Nyamasheke districts of the Western Province in Rwanda for the management of sick children aged 1 day to 14 years (inclusive). The intervention will be implemented in blocks of 10-12 (half intervention and half control) HFs (**Figure 6**). Each step will last for four months, with the first month serving as a phase-in period. To assess the primary and secondary outcomes in Phase 1 (i.e. antibiotic prescription and cure rate), final decision on referral, diagnoses and treatments at initial consultation (day 0) will be recorded by HWs electronically in intervention and control facilities. All children in Phase 1 of the study will also be followed-up by a phone call or SMS (or home visit) to their caregiver at day 7 to determine their final health status. The CRFs are presented in **Appendix A**.

Due to the pragmatic nature of the study, the design is adaptive, in that changes to the implementation may be incorporated during each of the three parallel cluster studies to account for issues encountered in monitoring data and feedback from the field. These changes apply to the implementation context (such as training, frequency or focus of monitoring visits, etc.) and exclude significant adaptations of the algorithm.

The primary outcome (antibiotic prescription rate) will be compared between intervention and control facilities within implementation blocks (e.g. group 1 will be compared with group 2, group 3 with group 4, etc.). To assess the secondary outcome (cure rate), the data from all intervention periods (groups 1, 3 and 5) and control periods (groups 2, 4 and 6) will be combined to achieve a sufficient sample size. Additionally, HFs within the same group will also be compared longitudinally (e.g. outcomes during control and intervention periods can be compared in groups 2 and 4).

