6.1 Analysis methods

Analyses will follow CONSORT guidelines (Campbell, Piaggio, Elbourne, & Altman, 2012; Piaggio et al., 2012; Schulz, Altman, & Moher, 2010; Zwarenstein et al., 2008). Outcomes will be described by arm using summary statistics. Baseline characteristics will be compared by study arm and by cluster study to ensure that the pragmatic allocation of health facilities and sequential rollout of the study did not introduce significant bias. Baseline characteristics which will differ between treatment arms within and over all clusters will be described using summary statistics.

Since the documentation of final treatment in both arms is part of the per protocol definition, only the PP population can be used for primary outcome analysis. The primary outcome will be evaluated using a random effects logistic regression model with the binary outcome variable of antibiotic prescription, with study arm and covariates at patient-level (e.g. age, sex) as fixed effects, and cluster (health facility) and patient included as random effects. Binary secondary outcomes will be evaluated in the same way. All estimates will be reported as odds ratios (ORs) with two-sided 95% confidence intervals (CI). The study will be deemed a success if antibiotic prescription at the initial consultation is 25% less in the ePOCT+ arm compared to the control arm, although we expect a greater reduction based on limited pilot data.

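### At 45% control prescribing, a single block of 5-6 facilities per arm has about 61-69% power for the SAP's 25% reduction, not the sufficient power SAP 3.3 claims

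*SAP*

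**What the plan says.** SAP 3.3 sizes Phase 1 for a 25% relative reduction in antibiotic prescription (35% to 26%), with 80% power, a two-sided test, 660 patients per facility and an intraclass correlation (ICC) of 0.025. It concludes: "0.05, we would require a minimum of 11 clusters per arm". The trial enrols 16 per arm.

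The same section then turns to the three implementation blocks. If control prescribing proves higher, with 45% given as the example, "each cluster study of 5-6 health facilities per study arm will be sufficiently powered to show a statistically significant reduction in the primary outcome". No effect size, ICC or power is attached to that sentence.

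Three other places bear on it:

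- SAP 6.1 sets success at a 25% reduction, then adds "although we expect a greater reduction based on limited pilot data". It gives no figure for the greater reduction.
- Protocol 4.1 states: "The primary outcome (antibiotic prescription rate) will be compared between intervention and control facilities within implementation blocks". It reserves combining the blocks for the cure outcome.
- SAP 3.4 plans an analysis of the primary endpoint after each block. Implementation changes may be made at that time.

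**The concern.** The block sentence names 45% as the control rate from which a single block is large enough. A reader will take the effect to be the 25% reduction set out just before it. A block has roughly half the 11 facilities per arm required at 35%, so moving the control rate to 45% would have to cut the requirement by about half. That is worth checking.

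The stakes lie in how block results are read. If the true reduction is 25% and blocks have well under 80% power, a non-significant block will be common. A team relying on SAP 3.3 could take it as a sign that the intervention, or its implementation in that block, had failed. The risk is greatest if the within-block comparison in Protocol 4.1 is treated as the primary one. Protocol 9.1 and SAP 3.3 size the whole arms, and Protocol 9.2 and SAP 6.1 compare study arms, so the documents do not agree on which comparison is primary.

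**Working it through.** **Inputs (SAP 3.3).** Cluster size m = 660; ICC = 0.025; two-sided alpha 0.05 (z = 1.96); power 80% (z = 0.8416); relative reduction 25%; 5 or 6 facilities per arm in a block; control rate 45%.

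**Design effect.** 1 + (660 − 1) × 0.025 = 17.475.

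**Formula.** Facilities per arm k = (1.96 + 0.8416)² × (p1q1 + p2q2) / (p1 − p2)² × 17.475 / 660, where q = 1 − p.

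**Reproducing the SAP's 11.** For 35% versus 26%:

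- (1.96 + 0.8416)² × (0.35 × 0.65 + 0.26 × 0.74) / 0.09² = 406.9 children per arm before clustering.
- 406.9 × 17.475 / 660 = 10.77, so 11. This agrees with the SAP.

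**Same formula at 45% control.** A 25% reduction takes 45% to 33.75%:

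- (1.96 + 0.8416)² × (0.45 × 0.55 + 0.3375 × 0.6625) / 0.1125² = 292.2.
- 292.2 × 17.475 / 660 = 7.74, so 8 per arm. A block has 5 or 6.

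**Power with k per arm.** Φ( |p1 − p2| / √[(p1q1 + p2q2) × 17.475 / (660k)] − 1.96 ):

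- k = 5: 61.5%
- k = 6: 69.4%
- k = 8: 81.3%

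**Dependence on the unstated effect, at 45% control.**

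| Intervention arm | 5 per arm | 6 per arm |
|---|---|---|
| 36% | 43.2% | 50.0% |
| 33.75% (25% reduction) | 61.5% | 69.4% |
| 30% | 86.2% | 91.6% |
| 26% | 97.6% | 99.1% |

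**What would give 80% power (5 / 6 per arm), changing one input at a time.**

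- Control rate, with a 25% reduction: 57.1% / 52.0%.
- Relative reduction, at 45% control: 30.8% / 28.2%.
- ICC, at 45% versus 33.75%: 0.0156 / 0.0191.

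**Variants, 45% control (5 / 6 per arm).**

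- Pooled variance: 61.0% / 68.9%; 8 per arm needed (7.81).
- The ratio 26/35 instead of exactly 25% (45% to 33.43%): 64.0% / 71.9%; 8 needed (7.30).
- Non-central t with 2k − 2 degrees of freedom: 50.8% / 60.5%; 9 needed.
- One-sided 0.05, as in Protocol 9.1: 72.8% / 79.5%; 7 needed. This variant gives 9 (8.49), not 11, for 35% versus 26%.

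None reaches 80% with 5 or 6 per arm.

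**Whole trial.** With 16 per arm at 35% versus 26%, power is 92.7%.

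**The case against.** The strongest reply is that the sentence never says 25%. It promises a significant reduction at 45% or higher, and SAP 6.1 expects an effect above 25%. If control prescribing were 45% and the intervention arm still reached the planned 26%, block power would be 98-99%. On that reading the sentence is undocumented rather than wrong.

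Part of this stands. The claim does hold for a large enough effect, and the figure of 3 to 4 missed blocks in 10 applies only if the true reduction is 25%. But no larger effect is given as the basis anywhere. The SAP ties the claim to a higher control rate, and 45% is too low for the one effect it does quantify.

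Two smaller points are also fair. The formula gives 11 only with the rounded 26%; an exact 25% reduction (26.25%) gives 11.43, so 12. Carrying the 26/35 ratio to 45% control raises block power by only two to three percentage points, and 8 per arm are still needed. The normal approximation is also generous with 8 or 10 degrees of freedom. That makes the shortfall larger, and it is a reason to name the method in any replacement text.

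**Conclusion.** The concern holds. For a 25% reduction from 45%, a block needs 8 facilities per arm, and one with 5 or 6 has 61.5% or 69.4% power (50.8% or 60.5% with a t reference). About 3 to 4 in 10 such blocks would miss a real 25% effect. This rests on the SAP's own 660 per facility, ICC of 0.025 and two-sided 0.05, and on reading the sentence with the only effect the SAP quantifies. A reduction of about 28-31%, a control rate of about 52-57%, or an ICC below about 0.016-0.019 would rescue the claim, but the SAP states none of these as a condition. The 16 versus 16 comparison, the sample size and the success rule are not affected. The point should be fixed because the documents plan block-level comparisons of the primary outcome.

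**What to change.** 1. In SAP 3.3, replace the block sentence with block power under a stated effect, ICC and method. With the normal approximation: about 61% (5 per arm) and 69% (6 per arm) at 45% control and a 25% reduction. Add that 80% is reached at a control rate of about 57% / 52%, or at 45% control with a reduction of about 31% / 28%. If a t reference is chosen instead, the figures are 51% / 60% power, a control rate of about 64% / 58%, or a reduction of about 35% / 31%.
2. If the larger reduction expected in SAP 6.1 is the basis, give its size and source and compute block power from it.
3. Reconcile Protocol 4.1 with Protocol 9.1 and 9.2 and SAP 3.3 and 6.1 by naming the 16 versus 16 comparison as the single primary analysis. Report block results as supportive estimates with cluster-adjusted confidence intervals.

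The cost is wording: one conditional power statement becomes less favourable. Sample size and success rule do not change. The edit to Protocol 4.1 would go through the amendment procedure in Protocol 11.5.

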3.4 Statistical interim analyses

Interim analyses for the primary endpoints will be performed after each of the cluster studies. As previously mentioned, minor implementation changes may be made throughout the study to adapt to issues discovered from the monitoring data and feedback from the field at the time of the interim analyses. The Principal Investigators may decide to terminate the study prematurely according to certain circumstances, such as ethical concerns that cannot be resolved, in case of safety of the participants being compromised (e.g. if the benefits no longer outweigh the risks), alterations in accepted clinical practice that make the continuation of the study unwise, or evidence of harm of the intervention. In case of premature study termination, the Rwanda National Ethics Committee will be notified as per local guidelines.

3.5 Timing of final analysis

The final analysis will be performed after all enrolled study subjects have the day 7 outcome measured.

4. Statistical principles

4.1 Adherence and protocol deviations

Adherence to the study protocol is assessed based on the percent of patients enrolled in the study for which the clinician entered the final treatment (or confirmed the absence of treatment).

Adherence is defined as: % adherence to the study protocol = (number of children for whom the final treatment was inputted / number of children enrolled in the study) * 100%

Descriptive statistics on the adherence (N, mean, SD, median, minimum, maximum) will be provided by study arm (intervention and control).

4.2 Analysis population definitions

Intention-to-treat population: This population includes all patients enrolled in the study, regardless of whether the HW used ePOCT+ (intervention arm), or entered the final treatment data in the eCRF (both arms).

Per-protocol population: This population only includes patients enrolled in the study for whom the clinician confirmed the final treatment (or absence of treatment) / referral status within the ePOCT+ tool (intervention arm) or in the eCRF (control arm).

Complete case set: All enrolled subjects (intervention or control) for whom day 7 clinical cure data was collected (i.e. excluding lost to follow-up patients).

Complete consultation set: All enrolled subjects (intervention or control) for whom at least information on treatments were collected at day 0.

5. Study population

5.1 Screening data

All patients presenting to the outpatient department of participating health facilities will be screened for eligibility. At the screening stage, the age of the patient and reason for coming to the health facility (acute vs. routine or chronic care visit) will be documented. The following summary data for the facility will be presented: the number of days during which screening has taken place, the number of patients recruited, the average number of patients recruited per day, the number of screened patients not recruited, and the reason for non-recruitment (e.g. non-eligibility vs. declined enrollment).

5.2 Eligibility

5.2.1 Health facility (cluster) eligibility

Health facility eligibility for the study is based on the health facility meeting all inclusion criteria and none of the exclusion criteria:

Inclusion Criteria:

- Government and NGO-supported government-designated primary health centers
- Located in Rusizi and Nyamasheke districts of the Western Province of Rwanda
- Seeing at least 19 children aged less than 5 years per week for IMCI services in 2019 (to facilitate participant recruitment)*

*Based on estimates from extrapolated data from HMIS.

Exclusion Criteria:

- Primary health posts
- Secondary and Tertiary HFs (district, regional, zonal and specialized hospitals)

5.2.2 Study population eligibility

A patient is eligible for the study if they meet all inclusion criteria and none of the exclusion criteria:

Inclusion Criteria:

- Aged 1 day (24 hours) to 14 years (inclusive)
- Presenting for an acute medical or surgical condition

Exclusion Criteria:

- Presenting for scheduled consultation for a chronic disease (e.g. HIV, TB, NCD, malnutrition)
- Presenting for routine preventive care (e.g. growth monitoring, vitamin supplementation, deworming, vaccination).
- Caregiver unavailable, unable or unwilling to provide informed consent (except for older children who can provide assent with an adult witness during the consenting process).

5.3 Recruitment

A CONSORT flow diagram will be used to summarize the number of patients throughout the study process.

5.4 Baseline characteristics

The baseline cluster (health facility) characteristics that will be summarized by study arm include:

- Number of health facilities by district
- Average number of patients seen per month by health facility
- Availability and readiness of basic health care services score based on the Rwandan Service Provision Assessment (median and IQR)

The baseline patient characteristics that will be summarized by study arm, and for the overall study include:

- Demographics: sex (number and percentage); age (median and IQR), age groups 0-2 months, 2 months - 5 years, 5-14 years (number and percentage)
- Medical history: Main reasons for consultation, history of fever (number and percentage)

Given the pragmatic nature of the study, and so as not to influence the normal management of patients and their outcome in the control arm, clinical signs and comorbidities will not be systematically collected in the control and intervention arm.

Baseline data will be compared across the study arms to confirm no bias due to lack of true randomization.

6. Main analyses

6.1 Analysis methods

Analyses will follow CONSORT guidelines (Campbell, Piaggio, Elbourne, & Altman, 2012; Piaggio et al., 2012; Schulz, Altman, & Moher, 2010; Zwarenstein et al., 2008). Outcomes will be described by arm using summary statistics. Baseline characteristics will be compared by study arm and by cluster study to ensure that the pragmatic allocation of health facilities and sequential rollout of the study did not introduce significant bias. Baseline characteristics which will differ between treatment arms within and over all clusters will be described using summary statistics.

Since the documentation of final treatment in both arms is part of the per protocol definition, only the PP population can be used for primary outcome analysis. The primary outcome will be evaluated using a random effects logistic regression model with the binary outcome variable of antibiotic prescription, with study arm and covariates at patient-level (e.g. age, sex) as fixed effects, and cluster (health facility) and patient included as random effects. Binary secondary outcomes will be evaluated in the same way. All estimates will be reported as odds ratios (ORs) with two-sided 95% confidence intervals (CI). The study will be deemed a success if antibiotic prescription at the initial consultation is 25% less in the ePOCT+ arm compared to the control arm, although we expect a greater reduction based on limited pilot data.

Effect modification of the primary outcome of antibiotic prescription will be performed in groups of patients where the highest reduction in antibiotic prescription is expected, and areas of extension of the content of the algorithm compared to the version tested in the previous ePOCT study. Effect modification by sex, age group (young infants ages 1 to 59 days, children aged 2 months to 5 years, and children aged 5 to 14 years), respiratory symptoms, fever without clinical source, gastrointestinal complaints (vomiting and diarrhea), skin problems, ear, nose and throat problems, will be assessed by incorporating an interaction term between the treatment arm and the respective variable, acknowledging that power will be low. Furthermore in order to adjust for potential imbalances in baseline characteristics between study groups, relevant baseline characteristics will be included as fixed effect variables in the final model. Baseline characteristic imbalance will be determined by statistical method (i.e., comparisons of treatment arms over all clusters and within clusters) and by consensus among the study analysis team.

The number of children lost to follow up may be quite high due to the difficult nature of phone follow-up at day 7, as found in previous studies with day 7 phone call lost to follow up rates of 13-25% (Christie et al., 2018; Hannigan, Chisale, Drew, Watson, & Gallagher, 2019; Nguhuni et al., 2017).

Comparatively, the proportion not cured at day 7 is expected to be quite low (3%). The use of a complete case analysis was therefore selected for the secondary outcome of day 7 clinical cure, as it would be the most conservative analysis. If we were to use the “enrolled set” and considered all day 7 lost to follow up as not being cured, this would dilute the difference between arms. Not considering lost to follow up cases as failures is also the approach used for similar studies with high number of LTF

and low proportion of outcomes (Källander et al., 2018). We may adjust the final model for further baseline variables (not already included as fixed effect variables) which are associated with missing outcome data (analogous to performing multiple imputation in the case of a single endpoint). As with the other fixed effect variables, baseline characteristic imbalances among patients lost to follow up will be determined by consensus among the study analysis team.

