Study design	
The primary intervention study will be conducted using a parallel-group cluster non-randomized controlled superiority trial study design implemented in two phases. Additional mixed-methods operational research will take place throughout the intervention period.
 
Phase 1: parallel cluster randomized controlled study in 32 health facilities
 
The ePOCT+ tool will be introduced sequentially using in three implementation blocks of 10-12 (half intervention and half control) facilities. Each of the parallel cluster study (implementation block) will last for approximately four months, with the first month serving as a phase-in period. The aim is to compare the effect of using ePOCT+ with

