Since the intervention takes place at the health provider level and their practices are influenced by the context of the health facility they are working in, randomization at health facility level rather than at HCW level or at individual patient level was chosen. The randomization of clusters (i.e. health facilities) will be performed on a 1:1 ratio. Thus, ePOCT+ will be provided to health workers (HWs) of 16 of the 32 selected primary health care facilities (intervention arm) in Rusizi and Nyamasheke districts, while the other 16 health facilities (HFs) will serve as controls (control arm). Sick children aged 1 day to 14 years (inclusive) will be managed in accordance with the study arm to which the HF they attend has been assigned. The comparator for Phase 1 will be routine care as currently implemented in Rwanda supplemented with equivalent clinical training given to the intervention arm. To assess the primary and secondary outcomes, final decision on referral, laboratory test results, diagnoses and treatments at initial consultation will be recorded by HCWs electronically in both arms (in the intervention arm integrated into the CDSA; in the control arm via a simple eCRF without any decision support); children will also be followed-up by a phone call or home visit to their caregiver at day 7 (range 6-14) to determine their clinical status. The study is considered as pragmatic since there are no major exclusion criteria to the population of interest, and the setting and organization of the health facilities remains mostly the same. The trial design is summarized below. Furthermore, in line with the pragmatic nature of the study, the design is adaptive, in that changes in the implementation across the three parallel cluster studies may be made based on monitoring data and feedback from the health facilities. These implementation changes (excluding significant adaptations to algorithm content) will be thoroughly documented and accounted for in comparisons across the three cluster studies.

PHASE 1

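### SAP 6.1 sets no small-sample rule for the arm effect: uncorrected intervals would carry about 6–7% two-sided error over 32 facilities and about 8–12% within a block

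*SAP*

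**What the plan says.** **Model and interval.** SAP 6.1 fits a logistic model with study arm and patient-level covariates as fixed effects and "cluster (health facility) and patient included as random effects". Binary secondary outcomes are handled the same way, and "All estimates will be reported as odds ratios (ORs) with two-sided 95% confidence intervals (CI". The section does not name an estimation method, a type of interval, a degrees-of-freedom rule, a small-sample correction or a facility-level alternative. Protocol 9.2 names none either and leaves further detail to the SAP.

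**Number of facilities.** SAP 3.1 gives the intervention to "16 of the 32 selected primary health care facilities (intervention arm"), with the other 16 as controls. The protocol synopsis introduces the tool in "three implementation blocks of 10-12 (half intervention and half control) facilities", so a block has 5–6 facilities per arm.

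**Block-level inference.** Protocol 4.1 states: "The primary outcome (antibiotic prescription rate) will be compared between intervention and control facilities within implementation blocks". The same section pools all blocks for cure. SAP 3.4 adds: "Interim analyses for the primary endpoints will be performed after each of the cluster studies". SAP 3.3 makes a claim for the case that control prescribing is at least about 45%: "each cluster study of 5-6 health facilities per study arm will be sufficiently powered to show a statistically significant reduction in the primary outcome". The SAP does not say which model the block analyses use. The 6.1 model is the only one it specifies for this outcome, so that is the natural reading.

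**The concern.** All children at a facility are in the same arm. The arm effect is therefore estimated from differences between facilities, and its precision depends on how well the between-facility variance is known. That variance is estimated on 30 degrees of freedom in the pooled analysis and on 8–10 in a block, however many children are enrolled.

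Software defaults for logistic mixed models commonly go wrong here in two ways. They refer the estimate to a normal rather than a t distribution, and maximum likelihood (ML) underestimates the between-facility variance. Both narrow the interval, and both matter more as facilities become fewer. What is at stake is mainly the credibility of the block-by-block results on the primary outcome. An unspecified method could also be chosen after the data are seen, in an open-label trial.

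**Working it through.** **Inputs.** SAP 3.3: 35% versus 26%, 80% power, two-sided alpha 0.05, 660 children per facility, intraclass correlation (ICC) 0.025, minimum 11 clusters per arm. SAP 3.1: 16 facilities per arm. Protocol synopsis: 10–12 facilities per block.

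**1. The plan's own figure.** Mean proportion 0.305.
- n per arm = [1.96·√(2·0.305·0.695) + 0.842·√(0.2275 + 0.1924)]² / 0.09² = 409.6, rounded up to 410.
- Design effect = 1 + 659·0.025 = 17.475.
- Clusters per arm = 410·17.475/660 = 10.86, rounded up to 11.

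The SAP figure reproduces. It uses normal critical values.

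**2. Error of uncorrected methods.** Take k facilities in two equal arms and a normal-theory comparison of facility log-odds. The correctly studentised difference T follows t on k−2 degrees of freedom under no effect. Each method rejects when |T| exceeds a cut-off c:
- ML variance with z: c = 1.96·√((k−2)/k), because ML divides by k rather than k−2. This gives 1.898, 1.789 and 1.753 for k = 32, 12 and 10.
- Profile likelihood: c = √((k−2)·(exp(1.96²/k) − 1)), giving 1.956, 1.942 and 1.936.
- REML-type variance with z: c = 1.96.
- t critical value on the ML standard error: c = t(0.975, k−2)·√((k−2)/k), with t = 2.04, 2.23 and 2.31.

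| Two-sided error at nominal 5% | k = 32 | k = 12 | k = 10 |
|---|---|---|---|
| ML Wald, z | 6.7% | 10.4% | 11.8% |
| Profile likelihood | 6.0% | 8.1% | 8.9% |
| REML-type variance, z | 5.9% | 7.8% | 8.6% |
| ML standard error, t | 5.7% | 6.9% | 7.3% |
| Corrected variance, t | 5.0% | 5.0% | 5.0% |

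**3. Simulation check.** A random-intercept logistic model was fitted by ML with adaptive quadrature to null data (35% in both arms, 660 per facility, ICC 0.025), with about 18,000 fits per case over logit-normal and beta facility effects. Errors for k = 32, 12 and 10:
- ML Wald with z: 6.7%, 10.6% and 11.9%.
- t on the ML standard error: 5.6%, 6.8% and 7.3%.
- Facility-level t-test: 4.9%, 5.0% and 5.1%.

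With an assumed ICC of 0.05, ML Wald gave 6.1%, 9.9% and 11.7%.

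**4. Power cost of the correction.** With c facilities per arm, δ = |p₁−p₂| / √[(p₁q₁ + p₂q₂)·17.475/(660c)]. Power by z is Φ(δ − 1.96). Power by t is the upper tail of the noncentral t on 2c−2 degrees of freedom beyond its critical value.

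| Scenario | δ | Power, z | Power, t |
|---|---|---|---|
| 35% vs 26%, 16 per arm | 3.41 | 92.7% | 91.0% |
| 35% vs 26%, 11 per arm | 2.83 | 80.8% | 76.8% |
| 45% vs 33.75%, 6 per arm | 2.47 | 69.4% | 60.5% |
| 45% vs 33.75%, 5 per arm | 2.25 | 61.5% | 50.8% |

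The pair 45% and 33.75% is a 25% relative reduction from the control rate in SAP 3.3 (0.45·0.75 = 0.3375). The formula of step 1 then asks for 295·17.475/660 = 7.81, so 8 facilities per arm even by z.

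**The case against.** The strongest reply is that the SAP prescribes neither ML, Wald nor z. A reader might infer that the plan commits itself to a 10–12% error in blocks, more than double the nominal rate. The documents do not support that. It is the result of one common default; the other two uncorrected methods give 7.8–8.9%. This part of the reply stands, so the size must be given as a range.

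The pooled analysis is only mildly affected: 5.9–6.7%, with 16 facilities per arm where the plan's calculation needs 11. This also stands.

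A reader might also infer that trial decisions hang on block significance. They do not, on the text. The SAP 3.3 sentence is conditional on a high control rate. SAP 3.4 ties the interims to minor implementation changes, lists ethics, safety, changed practice and harm as reasons to stop, and gives no efficacy boundary. The success criterion in SAP 6.1 is a 25% lower prescription figure without a significance threshold. The point is therefore about reported inference.

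Nor do the block figures carry over to day-7 cure, which Protocol 4.1 pools. An approximate check for 32 facilities (3% not cured, from SAP 6.1; assumed 530 children per facility and ICC 0.001–0.01) gives 6.4–6.8% with ML and z, again the mild case.

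Finally, SAP 3.3 does not name the reduction behind its block-power sentence, and SAP 6.1 expects more than 25%. A larger effect would raise block power, but 25% is the only reduction the sample-size section states.

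What does not stand is the idea that the omission is harmless. Protocol 4.1 commits to within-block comparison of the primary outcome, and no usual uncorrected method holds 5% there.

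**Conclusion.** The omission is real and should be corrected. Following SAP 6.1 with usual software defaults gives intervals for the arm effect that are too narrow: slightly in the pooled 32-facility analysis (about 6–7% error) and materially in blocks of 10–12 facilities (about 8–12%, depending on the method). It does not undermine the pooled primary result.

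The sizes rest on the SAP's cluster size and ICC, equal facility sizes, and the 6.1 model being used in blocks. The simulations leave out the patient random effect and patient-level covariates, which should have little influence on between-facility degrees of freedom. Facility-level adjusters or block terms would reduce those degrees of freedom further. Bias from the geographic, non-random allocation is a separate matter that no small-sample correction addresses.

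**What to change.** Amend SAP 6.1 to say that the test and 95% interval for the arm effect use a t distribution with facility-based degrees of freedom (facilities minus facility-level parameters) **together with** a between-facility variance corrected for bias, and name the procedure. The alternative is a facility-level t-test on covariate-adjusted proportions, with the effect scale stated because the SAP otherwise reports odds ratios. Say explicitly that the rule applies to the pooled analysis and to every block-level and interim comparison. Putting t critical values on an uncorrected ML standard error is not sufficient, because it leaves about 7% error per block.

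The text change is a sentence or two. At 16 per arm power falls by about 2 points (92.7% to 91.0%). At the planned minimum of 11 per arm it falls from 80.8% to 76.8%, so that minimum would become 12; the planned 16 still exceeds it. In blocks, at 45% versus 33.75%, the loss is about 9–11 points: 69.4% to 60.5% at 6 per arm and 61.5% to 50.8% at 5 per arm. The block-power statement in SAP 3.3 should therefore be removed, or restated with the reduction it assumes and power computed under the corrected test.
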